## Effect of a Digital Engagement Strategy on Healthcare Worker Mental Health and Well-being: A Randomized Controlled Trial

t-tests and generalized linear models that account for baseline measurements of PHQ-9 and GAD-7. Missing data will be assessed for patterns and multiple imputation will be used if deemed appropriate. Baseline covariates that are found to be imbalanced between arms may be adjusted for in the model if they were deemed to be potential confounders a priori to adjust for potential confounding and for efficiency gain. We will use all available PHQ-9 and GAD-7 scores on eligible patients from randomization through the last observation. A p<0.05 will be deemed statistically significant but emphasis will be placed on point estimates and confidence intervals. Secondary outcomes of mental healthcare utilization, satisfaction with connection to services, and qualitative feedback on mobile engagement will also be modeled using GEE with mean models specified based on the distribution of the specific outcome (e.g. Poisson or negative binomial for number of mental healthcare visits, logit for binary responses). Potential associations between system-level or regional level case burden and PHQ-9 and GAD-7 scores at baseline and over-time will be assessed with generalized linear models and GEE. Exploratory Aim 1: Statistical approach: The statistical approach for studying HTE will be to test for the statistical interaction between the intervention and race and separately by gender in the GEE models described above. Although our study was not designed specifically to detect HTE, if 20% of our trial participants are Black (based on targeted recruitment efforts), our study will achieve 80% power (assuming type I error of 0.05) to detect a 1.8 difference in mean GAD-7 scores and a 2.0 difference in mean PHQ-9 scores between arms at 6 months. We anticipate that at least 50% of participants will be female. Hence, our study is powered to detect a 1.2 difference in mean GAD-7 scores and a 1.3 difference in mean PHQ-9 scores between arms at 6 months among women. Aim 2: Power: no power calculation will be performed for this qualitative aim consistent with prior qualitative aims we will aim to interview 80 participants from Aim 1 and evaluate themes until saturation Analysis: Using thematic analysis, we will analyze HCW interview transcripts to identify recurring themes in attitudes and beliefs toward mental health, well-being, and mental health care or resources. Interview audio will be transcribed and uploaded into Nvivo software (available as a Penn resource). In total we plan for up to 80 semi-structured interviews, or until inductive thematic saturation is reached in each group meaning no new themes are emerging. Analysis of qualitative, semi-structured interviews utilizes a series of systematic steps in transcribing, developing a code for thematic content, and subsequent coding of interviews. A modified grounded theory approach will be used to evaluate interview transcriptions. Analysis will begin shortly after the first few interviews are completed. An emergent, iterative open coding process will be followed and two trained coders from the research team will jointly read five transcripts and draft the outline of a codebook. Each coder will then independently code five more transcripts and adjust the codebook as needed. We will review the codes, resolve discrepancies and finalize coding procedures. Following adjudication of any areas of discrepancy, the research team coders will be assigned batches of transcripts for independent coding, sharing 25% of the transcripts in each batch for ongoing inter-rater agreement assessment. We will review coding for interrater reliability, measured by Cohens kappa (0.8), and overall comprehensiveness. If a high kappa is not achieved, further double coding and refining of the code will continue. This approach to coding and analyzing qualitative data has been widely used. Strategies used to ensure reliability and validity in the qualitative data will include a comprehensive audit trail, checks between coders, team debriefing, and corroboration of findings across participants.

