## Effect of a Digital Engagement Strategy on Healthcare Worker Mental Health and Well-being: A Randomized Controlled Trial

separate outcomes that we will be evaluating. We aim to enroll 1275 participants with the anticipation that there will be 27.5% attrition.

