### *8.2 Procedures*

We will conduct a prospective two-armed randomized control trial to test the effect of tailored mental health support on self-reported HCW mental health (anxiety and depression) during the response and recovery phases of the COVID-19 pandemic. The control group will have access to Cobalt which is usual care for all Penn Medicine employees. The Cobalt platform is web-based and is accessible from any device or desktop. Cobalt uses contextual surveys and evidence-based assessments to triage individual users to curated content and appropriate group or individual support. The current, and usual care, model is a digital version of what exists at other institutions where resources are available for staff to access wellness and mental health services. The usual care Cobalt model requires staff to personally initiate multiple steps: 1) identify a personal need for support, 2) know where to seek support and care, 3) schedule an appointment, and 4) attend the appointment. In this context, the individual has to pull the resources they need and there may be several barriers to completing each step. This is particularly relevant as mental health conditions can compromise insight, motivation, and decision making, thereby making self-directed engagement in care (pull) more challenging. The RCT will compare this pull model with a new model, the intervention named Cobalt+, which will proactively reach out to and engage individuals in order to reduce barriers in identifying a need for and accessing mental health care. The intervention group will have access to the same Cobalt resources as those in the usual care group but will also receive a comprehensive suite of services including: 1) monthly automated text messaging reminders and links to Cobalt resources 2) intermittent mental health assessments (PHQ-9, GAD-7) at enrollment, month 2, month 4 and month 6 which triage individuals to an opt-out appointment with a resilience coach, psychotherapist, or psychiatrist based on their results. Of note, all employees will have access to Cobalt whether they are in the study or not. Through the proposed RCT we will evaluate whether the intervention, a proactive model of care delivery (Cobalt+) impacts the primary outcome measure (depression and anxiety) and secondary outcome measures (well-being, satisfaction with access to care, and measures of work productivity [e.g. absenteeism]). Difficulties due to health conditions mental health domains will be assessed at the month 9 follow up survey.

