
### **9. Analysis Plan**

We will conduct an intent to treat (ITT) analysis. The ITT analysis will include all randomized participants in the groups to which they were randomly assigned. Baseline demographic and clinical characteristics will be reported as frequency and percent for categorical variables and median and distribution for continuous variables. We will compare baseline characteristics between intervention and control arms using t-tests for continuous variables and chi-squared tests for categorical variables. The goal of these comparisons will be to determine if the two arms are balanced on baseline variables after randomization. Our primary analysis will focus on the difference in PHQ-9 and GAD-7 scores at 6 months between the two arms. We will estimate and test differences in means between arms using two- sample

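### Section 9 gives each 6-month primary outcome two unranked tests and plans no missing-not-at-random sensitivity analysis despite 27.5% expected attrition

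*Combined protocol and SAP*

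**What the plan says.** Section 9 (Analysis Plan) of the final protocol fixes the contrast: "Our primary analysis will focus on the difference in PHQ-9 and GAD-7 scores at 6 months between the two arms". For the method it says "We will estimate and test differences in means between arms using two- sample" and continues "t-tests and generalized linear models that account for baseline measurements of PHQ-9 and GAD-7". The two methods are joined by a plain conjunction, and no sentence calls one primary and the other supportive. Significance is set at p<0.05, with weight placed on estimates and intervals.

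On the analysis set: "The ITT analysis will include all randomized participants in the groups to which they were randomly assigned". On missing data: "Missing data will be assessed for patterns and multiple imputation will be used if deemed appropriate". And: "We will use all available PHQ-9 and GAD-7 scores on eligible patients from randomization through the last observation". Section 9 states no missing-data assumption, no imputation model and no sensitivity analysis for data missing not at random.

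Section 7.3 (Accrual) says: "We aim to enroll 1275 participants with the anticipation that there will be 27.5% attrition". It does not say at which time point. It also sets type I error at 2.5% per outcome, which differs from the p<0.05 in Section 9.

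Section 8.2 (Procedures) lists "intermittent mental health assessments (PHQ-9, GAD-7) at enrollment, month 2, month 4 and month 6" as part of the Cobalt+ package. Section 7.5 describes three paid surveys for all participants: enrollment, 6 months and 9 months.

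**The concern.** Two tests of one contrast can give two answers. Without an order between them, which one carries the conclusion can be decided after the data are seen.

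The tests also respond differently to dropout. A t-test on completers is biased if dropout depends on baseline severity in one arm and not the other. The baseline-adjusted model is not, provided the baseline relation is modelled correctly.

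If those who leave differ from what their baseline predicts, and do so differently by arm, both tests and baseline-only imputation are biased alike. The pattern check may flag unequal dropout, but observed data cannot rule this mechanism out.

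Finally, if the sentence on using all available scores is applied to the 6-month comparison, mid-study scores may come from one arm only.

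**Working it through.** **Inputs.** From Section 7.3: N = 1275, attrition 27.5%, and a stated SE of 5.0 (PHQ-9) and 4.6 (GAD-7), read here as SDs. Assumed: 1:1 allocation, two-sided tests, all attrition present at month 6, and baseline-to-6-month correlation r = 0.5 to 0.7. Then 1275 × 0.275 = 350.6 lack a score and 1275 × 0.725 = 924.4 have one, about 462 per arm.

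**The plan's own figures.** Section 9 gives power only for subgroups (80%, alpha 0.05). Detectable difference = SD × (1.960 + 0.842) × √(2/n per arm).

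| Subgroup | Stated GAD-7 / PHQ-9 | 1,000 completers | 924 completers |
|---|---|---|---|
| Black participants, 20% | 1.8 / 2.0 | 1.82 / 1.98 | 1.90 / 2.06 |
| Women, 50% | 1.2 / 1.3 | 1.15 / 1.25 | 1.20 / 1.30 |

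The match, with no baseline adjustment, supports reading the SE as an SD. It also shows that the adjusted model is not self-evidently the primary method.

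**Either test significant.** Under no effect the two statistics correlate √(1 − r²). The chance that at least one rejects, from the bivariate normal:

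| r | Correlation of statistics | Nominal 5% | Nominal 2.5% |
|---|---|---|---|
| 0.5 | 0.866 | 7.3% | 3.8% |
| 0.6 | 0.800 | 7.8% | 4.0% |
| 0.7 | 0.714 | 8.3% | 4.3% |

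**Precision (alpha 0.05, 80% power).** PHQ-9 t-test: 5 × 2.802 × √(2/462) = 0.92. The adjusted model multiplies this by √(1 − r²), giving 0.80, 0.74 and 0.66 for r = 0.5, 0.6 and 0.7. For GAD-7 the t-test gives 0.85 and the model 0.73 to 0.61.

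**Dropout tied to baseline in Cobalt+ only, no true effect** (3,000 simulated trials). The t-test bias is r times the shift in completers' mean baseline.

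| Missing | Log-odds per baseline SD | t-test bias, r = 0.5 / 0.7 | t-test rejection at 5% |
|---|---|---|---|
| 27.5% | 0.3 | −0.20 / −0.28 | 9% / 13% |
| 27.5% | 0.5 | −0.33 / −0.46 | 16% / 29% |
| 20% | 0.3 | −0.15 / −0.21 | 8% / 10% |
| 20% | 0.5 | −0.24 / −0.34 | 12% / 20% |

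The adjusted model stays within 0.01 of zero and rejects about 5% of the time. With log-odds 0.5 in both arms, the t-test bias is 0.00.

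**Missing not at random.** Bias = missing share × d, where d is the between-arm difference in how far dropouts depart from what baseline predicts. At 27.5% this is 0.275 × 1 = 0.28 points per point of d; at 20% it is 0.20; at d = 0 it is zero. An estimated 1.0-point benefit from the adjusted model loses p<0.05 at d = (1.0 − 1.96 × 5 × √(1 − r²) × √(2/462)) / 0.275, which is 1.61, 1.76 or 1.96 for r = 0.5, 0.6 or 0.7.

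**Months 2 and 4 scores in Cobalt+ only.** Simulated with correlations 0.6 (baseline with follow-up) and 0.7 (month 4 with month 6), 27.5% missing, no true effect. Dropout log-odds are 0.3 / 0.5 / 1.0 / 1.5 per SD of the month-4 score.

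| Dropout depends on month-4 score in | Imputation using Cobalt+ month 4 | Baseline-adjusted model |
|---|---|---|
| Both arms, same rule | 0.16 / 0.28 / 0.49 / 0.64 | within 0.01 of zero |
| Cobalt+ only | within 0.005 of zero | −0.17 / −0.28 / −0.50 / −0.64 |
| Control only (0.5) | about 0.27 in size | about 0.27 in size |

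Neither including nor excluding these scores is safe in every case.

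**The case against.** - **Nobody says either test is enough.** This stands. A reader might infer that the plan permits a claim on whichever test succeeds, but no passage says so, and Section 9 puts weight on estimates and intervals. The 7.3% to 8.3% is therefore the worst reading. Two methods still give two estimates and two intervals, and the same sentence keeps a p-value threshold.
- **Disagreement between the tests is mostly the model's precision gain.** This stands too. At an assumed true PHQ-9 effect of 0.75 points and alpha 0.05 they disagree 18% to 29% of the time, but 10% to 13% at 1.0 and about 2% at 1.3. At 0.75 nearly all of it is significance by the adjusted model alone. That is a reason to make the model primary, not evidence of error.
- **Differential dropout is hypothetical.** Agreed. Payments and reminders are described for participants generally. Assessments and triage in one arm make unequal retention plausible, but no figure in the documents shows it.
- **The missing-not-at-random formula fits any trial with dropout.** True, and nothing in the documents bounds d. That is why a tipping-point analysis, not a correction, is the remedy.
- **The months 2 and 4 scores should simply be barred.** A reader might infer this because they come from one arm. The documents do not support a ban. The sentence on all available scores may refer to the over-time analyses in the same section, and leaving the scores out is biased by a similar amount if dropout depends on them in Cobalt+ only.

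**Conclusion.** The concern holds in limited form. The primary contrast is specified but the primary test is not, and no planned analysis shows how far missing-not-at-random dropout could move the result. This should be fixed, though it does not invalidate the trial.

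The firm part is textual: two unranked methods, optional imputation and no such sensitivity analysis. The sizes rest on assumptions: r of 0.5 to 0.7, 1:1 allocation, the full 27.5% missing at month 6, and an SD of 5.0 taken from a cited sample with mean PHQ-9 14.0. This trial sets no symptom threshold for entry, so its spread may differ, and every point figure scales with it. The bias figures describe what could happen under stated dropout rules, not what the documents show will happen.

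**What to change.** In Section 9, replace the sentence naming the two methods with text to this effect:

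> For each outcome the sole primary analysis is the generalized linear model of the 6-month score on arm and baseline score, assuming data are missing at random given the model covariates. The unadjusted two-sample t-test is supportive. A delta-adjusted tipping-point analysis, with delta varied separately in each arm, will show how large a departure from that assumption would change the conclusion.

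Then state whether the use of all available scores applies to the 6-month comparison. Because months 2 and 4 are listed only for Cobalt+, report multiple imputation with and without those scores as a sensitivity check.

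Naming the model removes the second primary test, gains precision and deals with dropout that depends on baseline. The tipping-point analysis shows, but does not correct, the effect of missing-not-at-random dropout. The paired imputations show whether the one-arm scores matter, without presuming which result is right.

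The cost is revised wording and a little more analysis and reporting. No new data are needed.

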### 6.3 Study Duration

The RCT will compare this pull model with a new model, the intervention named Cobalt+, which will proactively reach out to and engage individuals in order to reduce barriers in identifying a need for and accessing mental health care. The intervention group will have access to the same Cobalt resources as those in the usual care group but will also receive a comprehensive suite of services including: 1) monthly automated text messaging reminders and links to Cobalt resources 2) intermittent mental health assessments (PHQ-9, GAD-7) at enrollment, month 2, month 4 and month 6 which triage individuals to an opt-out appointment with a resilience coach, psychotherapist, or psychiatrist based on their results. Of note, all employees will have access to Cobalt whether they are in the study or not. Through the proposed RCT we will evaluate whether the intervention, a proactive model of care delivery (Cobalt+) impacts the primary outcome measure (depression and anxiety) and secondary outcome

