### *7.5 Subject Compensation*

To promote retention, participants will be emailed up to 4 times and texted (up to three times) to nudge survey and assessment completion. For compensation, each participant will receive up to \$200: \$50 at enrollment, \$75 at 6 months and \$75 at 9 months for 3 total surveys. Submission for subject reimbursement will occur immediately upon completion of surveys and assessments and occur through the Way to Health platform which facilitates timely payment. Each participant will receive \$50 for interview completion.

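### Does using all available PHQ-9 and GAD-7 scores bias the arm comparison when months 2 and 4 appear only on the Cobalt+ schedule?

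*Combined protocol and SAP*

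**What the plan says.** Section 9 of the final protocol sets the primary target: "Our primary analysis will focus on the difference in PHQ-9 and GAD-7 scores at 6 months between the two arms". The tools are two-sample t-tests and generalized linear models adjusted for the baseline score. Later in the same section comes the sentence at issue: "We will use all available PHQ-9 and GAD-7 scores on eligible patients from randomization through the last observation". It lists no visits and mentions no term for month.

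GEE enters for the secondary outcomes, which "will also be modeled using GEE with mean models specified based on the distribution of the specific outcome". It is also named for the association of scores with regional case burden, and for the exploratory subgroup work, which will "test for the statistical interaction between the intervention and race and separately by gender in the GEE models described above".

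On the schedule, Section 6.3 says: "The intervention group will have access to the same Cobalt resources as those in the usual care group but will also receive" a set of extra services. Section 8.2 gives the same list, which includes "intermittent mental health assessments (PHQ-9, GAD-7) at enrollment, month 2, month 4 and month 6 which triage individuals". For control, Section 8.2 says: "The usual care Cobalt model requires staff to personally initiate multiple steps". Section 7.5 pays every participant at enrollment, 6 months and "9 months for 3 total surveys".

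**The concern.** Read together, these sections suggest that Cobalt+ participants contribute PHQ-9 and GAD-7 scores at months 2, 4 and 6, while controls contribute them only at the common surveys. If every score went into one repeated-measures model with an arm term and no month term, the Cobalt+ average would sit earlier in follow-up than the control average. Any drift in symptoms common to both arms would then appear as an arm difference.

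Drift is plausible, because the trial runs through the response and recovery phases of a pandemic. The race and gender interaction tests are to use GEE models whose occasions and time terms are not set out. At stake would be a false arm effect, in either direction, in an analysis beside the primary one.

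**Working it through.** The plan prints no figure on this point, so the check has two parts: which comparisons the plan commits to, and how large the distortion would be in a model that pools all scores.

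**What the plan commits to.** The primary contrast is at 6 months, when both arms are surveyed. A t-test or baseline-adjusted model on month-6 scores has one occasion per person, so time and arm cannot mix. The exploratory text in Section 9 states its detectable differences as arm differences at 6 months, for Black participants and again for women. The usual two-group formula with one score per person returns those figures, using the 1,250 enrolled and 20% attrition of the earlier protocol version (1,000 completers), and SDs of 4.6 and 5.0 (printed as SE in Section 7.3, read here as SD):

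- Black participants, 100 per arm: (1.960 + 0.842) × 4.6 × √(2/100) = 1.82 and (1.960 + 0.842) × 5.0 × √(2/100) = 1.98; printed 1.8 and 2.0.
- Women, 250 per arm: 1.15 and 1.25; printed 1.2 and 1.3.

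Both the wording and the arithmetic point to a single month-6 score.

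**Size in a pooled model without month.** Let both arms fall by D points by month 6, with no treatment effect. The shift is the Cobalt+ mean minus the control mean, so a positive value makes Cobalt+ look worse.

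| Control months | Cobalt+ months | Linear fall | Fall complete by month 2 |
|---|---|---|---|
| 6 | 2, 4, 6 | (6 - 4)/6 = +0.333 D | 0 |
| 6, 9 | 2, 4, 6, 9 | (7.5 - 5.25)/6 = +0.375 D | 0 |
| 0, 6 | 0, 2, 4, 6 | (3 - 3)/6 = 0 | 0.5 - 0.75 = -0.25 D |
| 0, 6, 9 | 0, 2, 4, 6, 9 | (5 - 4.2)/6 = +0.133 D | 2/3 - 4/5 = -0.133 D |

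A linear fall that stops at month 6 gives 1 - 0.75 = +0.25 D in the second row. Size and sign therefore depend on the trend shape and on whether baseline counts as an outcome.

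**Rejection rates.** Inputs: 1,275 × (1 - 0.275) = 924 completers (Section 7.3), or 462 per arm if allocation is equal; SD 5; an assumed within-person correlation of 0.6; two-sided 5%. These come from 3,000 simulated trials per scenario, with an exchangeable GEE, baseline as covariate and a linear fall:

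| D | 6 vs 2, 4, 6, no month | 6, 9 vs 2, 4, 6, 9, no month | Month as category |
|---|---|---|---|
| 0 | 5% | 5% | 5% |
| 1 | 30% | 46% | 5% |
| 2 | 82% | 95% | 5% |

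With month as a category, only Cobalt+ informs the month-2 and month-4 terms. The arm coefficient then comes from occasions observed in both arms, and its expected value is zero in every row of the first table.

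**Race interaction.** These results come from 2,000 simulated trials per scenario, with 20% Black participants and months 2, 4, 6 against 6. A common trend cancels out of the interaction, and rejection is 5-6%. A distortion needs trends that differ by subgroup. An assumed fall of 2 points against 1 gives a shift of about (2 - 1)/3 = 0.33 (simulated 0.34, rejection 9%). An assumed 3 against 1 gives about 0.67 (simulated 0.67, rejection 21%). Subgroup-by-month terms bring rejection back to 5-6%.

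**The case for a change.** The strongest case for a change is that the sentence stands in the paragraph on the PHQ-9 and GAD-7 analysis and could be followed literally. A GEE of these scores is implied by the subgroup tests, a pandemic-era trend is likely, and a literal pooled fit could reject far above 5%. With 27.5% attrition expected and multiple imputation left to later judgment, interim scores from one arm could also enter the imputation. Controls who assess themselves on Cobalt when they feel unwell might add a selected set of scores, which month terms alone would not correct. New wording costs little.

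Part of this stands. The plan does not say which occasions enter which model, and month should be in any repeated-measures fit. The rest is weaker:

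- The high rejection rates belong to a pooled main arm effect that no section describes.
- That controls have no month-2 or month-4 scores is a fair inference but is not stated. The Cobalt+ list also contains enrollment and month 6, when controls are surveyed too, and Section 7.4 describes a short survey message to participants with no arm restriction.
- Whether self-initiated control scores reach the dataset is not stated, and any size for that effect rests on invented rates.
- The imputation worry comes with no calculation, since all simulations used complete data.
- Barring Cobalt+ month-2 and month-4 scores from the main analysis would be a trade-off rather than a correction. They can inform missing month-6 scores, and an arm-by-month contrast read at month 6 showed bias of about zero (0.004, rejection 5.1%) with interim scores included.

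**Conclusion.** No change to the plan is needed. The sentence on all available scores can be read as ordinary intent-to-treat wording about keeping partial data, and the contrast the plan commits to is at 6 months, where both arms are measured. Done that way, the primary result carries no distortion from the unequal schedule, and the race interaction test stays at 5-6% under a common trend.

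A bias arises only if an analyst pools all scores and omits month. In the cases worked above it then lies between -0.25 and +0.375 of the common change by month 6, and is zero in several of them. Month and arm-by-month terms, with subgroup-by-month for the exploratory tests and the contrast read at month 6, are the standard way to fit such a model, so this is a gap that analysts fill sensibly.

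The conclusion rests on the primary analysis using month-6 scores. The illustrative sizes rest on assumed trends, a correlation of 0.6, equal allocation and the printed 5.0 being an SD.
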